#### **Full Analysis Set:**

The FAS contains the data of each eye in the SES for which data has been collected for the primary performance endpoint.

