Statistical methods:	The primary performance endpoint is defined as achievement of monocular UCNVA of Snellen equivalent 20/40 or better at 40 cm at Visit 5 (6 months after implantation) in equal to or greater than 75% of implanted eyes (responder rate). The analysis will be performed on all	

STAAR Surgical Company Study #CP17-01		
	eyes.	
	The implant procedure is defined as successful if the responder rate is equal to or greater than 75%. The corresponding statistical hypothesis is therefore as follows:	
	H 0 (null hypothesis): $\pi < 0.75$	
	H a (alternative hypothesis): $\pi \ge 0.75$	
	where $\pi$ is the true proportion of eyes that achieve the performance endpoint at 6 months postoperative (6-month responder rate). Fleming's two-stage design was used to optimize the sample size while allowing for early termination due to rejecting the null hypothesis. It is expected that 90% of eyes will achieve the performance endpoint and the sample size was therefore conservatively determined based on an 87.5% responder rate.	
	In the first stage, 27 patients (54 eyes) will be evaluated. If there are 43 or less response the trial will be stopped for futility since the likelihood of still obtaining a significant result is too low to continue the study under ethical considerations. If there are 48 or more responses the trial will be stopped and the null hypothesis rejected as enough statistical evidence has been accrued to determine that, within the certainty of the controlled one-sided type I error probability of 2.5%, the true responder rate is not lower than 75%.	
	Otherwise, 16 additional patients (32 eyes) will be recruited for a total of 43 patients (86 eyes). The null hypothesis will be rejected if 73 or more responses are observed among the 86 eyes. This design yields a one-sided type I error probability of 2.5% and a power of 80% if the true response rate is 87.5%.	
	Summaries for continuous variables will include the number of non- missing observations, mean, standard deviation (SD), median, minimum, and maximum. Summaries for discrete variables will include the tabulation of frequencies and percentages.	

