# 3.0 STUDY DESIGN

#### 3.1 Description of Study Design

This is a prospective, open-labeled, multi-site evaluation of clinical performance of the CE-Marked EDOF ICL for the improvement of UCNVA. Approximately 48 subjects who meet all eligibility criteria will undergo phakic IOL implantation in both eyes. All eyes will be followed for 6 months after surgery.

The first eye implanted with the study lens and the appropriate time for fellow eye implantation will be determined by the medical judgement of the Investigator. All eyes will be analyzed for safety and performance.

The subject will have completed the entire study when the study lenses have been implanted bilaterally and the Sponsor receives completed case report form (CRF) documentation for all visits. A Study Exit CRF for each eye must be completed for all subjects enrolled in the study.

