#### 3.2.3 Subject Discontinuation

A subject may be discontinued (at the discretion of the Investigator, the Sponsor and/or the EC) prior to the final study visit for several reasons, including, but not limited to:

- voluntary withdrawal
- death
- surgical complication preventing implantation of the study lens
- explant of the study lens(es)

If the study lens is explanted, a minimum of one post-explant visit should be completed to record safety measures for the subject (e.g., BCDVA, cataract/lens evaluation, endothelial cell count, etc.).

Prior to discontinuing a subject, every effort should be made to contact the subject, schedule a final study visit, and obtain as much follow-up data as possible.

Adverse events will be followed as described in Section 6.3.5. Subject withdrawals will be documented clearly on the source document and applicable CRF.

Only subjects who do not receive successful bilateral implantation MAY be replaced. Subjects who are discontinued from the study following treatment will not be replaced.

Discontinued subjects should be followed outside of the study protocol according to the Investigator's normal postoperative standard of care.

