#### 7.2 Study Endpoints

#### 7.2.1 Performance Endpoints

The primary performance endpoint is defined as achievement of monocular UCNVA of Snellen equivalent 20/40 or better at 40 cm at Visit 5 (6 months after implantation) in equal to or greater than 75% of implanted eyes (responder rate).

Fleming's two-stage design was used, which enables early termination of the study at an interim analysis for futility or performance. Here, an interim analysis will be performed with the results obtained from 27 subjects (54 eyes). If there are 43 or less responses, the trial will be stopped for futility since the likelihood of still obtaining a significant result is too low to continue the study under ethical considerations. If there are 48 or more responses observed at the interim analysis, the trial will be stopped and the null hypothesis rejected as enough statistical evidence has been accrued to determine that, within the certainty of the controlled one-sided type I error probability of 2.5%, the true responder rate is greater or equal to 75%.

Otherwise, 16 additional patients (32 eyes) will be recruited for a total of 43 patients (86 eyes). The null hypothesis will be rejected if 73 or more responses are observed among the 86 eyes. This design yields a one-sided type I error probability of 2.5% and a power of 80% if the true response rate is 87.5%.

Secondary performance endpoints include the following:

- Percentage of implanted eyes achieving monocular UCNVA of Snellen equivalent 20/40 or better at 40 cm at Visit 3 and 4 (1 and 3 months after implantation respectively)
- Change from baseline in monocular uncorrected intermediate visual acuity (UCIVA) at 80 cm at postoperative Visit 3, 4 and 5
- Change from baseline in monocular UCNVA at 40 cm at postoperative Visit 3, 4 and 5
- Change from baseline in monocular distance corrected intermediate visual acuity (DCIVA) at 80 cm at postoperative Visit 3, 4 and 5
- Change from baseline in monocular distance corrected near visual acuity (DCNVA) at 40 cm at postoperative Visit 3, 4 and 5
- Change from baseline in binocular UCNVA at 40 cm at postoperative Visit 3, 4 and 5

There are no prespecified performance targets for secondary performance endpoints. 95% confidence limits will be calculated for all secondary performance endpoints.

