#### Analysis sets:

The analyses of the primary and secondary performance endpoints will be based on the Full Analysis Set (FAS) and Per Protocol Set (PPS). Safety analyses will be based on the Safety Evaluation Set (SES) and FAS. Further analyses will be based on the FAS and PPS.

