#### Safety Evaluation Set:

The SES contains the data of each eye implanted with the study lens.

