#### Per Protocol Set:

The PPS contains data of each eye in the FAS without major protocol deviations. Protocol deviations are further classified in the SAP.

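### The primary endpoint is a rate of implanted eyes, but the performance analysis sets allow an eye explanted before Visit 5 to leave the denominator, with no stated rule for counting it

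*Combined protocol and SAP*

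**What the plan says.** Section 7.2.1 and the Synopsis define the primary endpoint as UCNVA of 20/40 or better at Visit 5 "in equal to or greater than 75% of implanted eyes (responder rate"). Section 7.5 (Analysis sets) then says: "The analyses of the primary and secondary performance endpoints will be based on the Full Analysis Set (FAS) and Per Protocol Set (PPS").

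The three sets are nested:
- **SES:** "The SES contains the data of each eye implanted with the study lens". It is used for safety only.
- **FAS:** "The FAS contains the data of each eye in the SES for which data has been collected for the primary performance endpoint".
- **PPS:** "The PPS contains data of each eye in the FAS without major protocol deviations".

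Section 3.2.3 lists explant as a reason for discontinuation before the final visit. After explant, "a minimum of one post-explant visit should be completed to record safety measures for the subject". UCNVA is not among the examples of what to record. The section also asks for as much follow-up data as can be obtained before a subject is discontinued, and it does not replace subjects discontinued after treatment.

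The decision counts in Sections 7.2.1 and 7.5 are fixed: 43 or fewer, or 48 or more, of 54 eyes at the interim, and 73 of 86 at the end. Section 7.3 allows for 10% attrition by enrolling 96 eyes. Section 7.0 leaves further detail to a separate SAP, which is not in the supplied text.

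**The concern.** The trial has one arm and is judged against a fixed 75% goal, so whatever is left out of the denominator bears directly on the conclusion. Removal of the lens is plausibly a failure of a lens-performance endpoint. Under the FAS rule such an eye can be treated as if it had never been implanted. If it was measured after the lens came out, the supplied text does not say whether that reading stands as a response, a non-response or neither.

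There is a related gap. The final bound is given for 86 eyes only, but if attrition falls short of 10% there will be more than 86 measured eyes, up to 96, and no bound for them.

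On the natural reading that primary endpoint data means a Visit 5 value, the FAS rule also discards Visit 3 and Visit 4 results from eyes that have no Visit 5 result.

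**Working it through.** **Inputs from the plan.** Null rate 0.75 and design rate 0.875. Stage 1 has 54 eyes, with a stop at 43 or fewer or at 48 or more. Stage 2 adds 32 eyes, and success needs 73 or more of 86 (Sections 7.2.1, 7.3 and 7.5). **Assumptions.** The share of eyes dropped is not in the documents; 1%, 2% and 3% are used. Eyes are treated as independent, as in the plan's own design.

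**1. The plan's own figures.** With X1 responders among the first 54 eyes and X2 among the next 32,

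P(success) = P(X1 ≥ 48) + Σ over x = 44 to 47 of P(X1 = x) × P(X2 ≥ 73 − x).

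- At 0.75: 0.0096 + 0.0136 = 0.0232, within the stated 2.5%.
- At 0.875: 0.4799 + 0.3372 = 0.8171, against the stated 80%.

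The design reproduces.

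**2. Effect of dropping eyes.** Let m be the share dropped and q their response rate. If the rate among all implanted eyes is 0.75, the rate among measured eyes is (0.75 − m·q)/(1 − m). For m = 1% and q = 0 this is 0.75/0.99 = 0.7576. Putting each rate into the formula in step 1, with exactly 54 and 86 measured eyes, gives:

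| Share dropped | Measured rate, all failures | False success | Measured rate, half respond | False success |
|---|---|---|---|---|
| 0 | 0.7500 | 2.3% | 0.7500 | 2.3% |
| 1% | 0.7576 | 3.3% | 0.7525 | 2.6% |
| 2% | 0.7653 | 4.6% | 0.7551 | 2.9% |
| 3% | 0.7732 | 6.3% | 0.7577 | 3.3% |

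**3. One eye at the final bound (single-stage exact figures).** 73/86 = 84.9%, with one-sided p = 0.019 and 95% lower limit 75.5%. Restoring one excluded failure gives 73/87 = 83.9%, with p = 0.032 and lower limit 74.5%, below the goal.

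**4. Keeping 73 with more than 86 eyes.** With the first stage unchanged, the two-stage error at 0.75 is 3.3% with 87 eyes, 4.6% with 88, 6.2% with 89 and 7.9% with 90.

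**5. Bounds that hold 2.5% for independent eyes.** With the first stage unchanged, the smallest final counts are 73/86, 74/87, 75/88, 76/89, 77/90, 77/91, 78/92, 79/93, 80/94, 80/95 and 81/96 (errors 1.7% to 2.5%).

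**6. Dependence on independence.** If each subject contributes two eyes with an assumed correlation of 0.3, 0.5 or 0.8, the error is 4.2%, 5.7% or 7.8% for 73/86, and 4.2%, 5.6% or 7.7% for 81/96.

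**The case against.** **Wording about all eyes.** A reader might see an outright contradiction with the Synopsis ("The analysis will be performed on all", completed after the page break by the word eyes) and with Section 3.1 ("All eyes will be analyzed for safety and performance"). The text does not force that. In Section 3.1 the sentence follows one about the first and fellow eye, and both places can mean both eyes of each subject. The clear conflict is between implanted eyes in the endpoint and the FAS definition. That stands.

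**Missing data in general.** A reader might infer that any missing eye inflates the rate. Withdrawals and losses do so only if they respond less often than measured eyes. Some explanted eyes may also be measured and stay in the FAS. The larger figures need every dropped eye to be a failure, and the documents give neither an explant rate nor a breakdown of the 10% attrition. This limits the size that can be claimed, not the existence of the gap.

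**The interim count.** A reader of Section 7.3, which enrols 54 eyes before the interim, might conclude that fewer than 54 will be analysed there. The Synopsis and Section 7.2.1 tie the interim to 54 eyes evaluated or with results. The passages need reconciling; they do not establish a shortfall.

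**The SAP.** It may contain a rule for explanted eyes. But the FAS is defined in the protocol itself, so a SAP rule that keeps every implanted eye would still have to be reconciled with it.

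**Conclusion.** The concern holds in this form: the endpoint counts implanted eyes, the sets used for performance keep only eyes with endpoint data, and an eye explanted before Visit 5 can fall between the two with no stated rule. The direction of bias is upward if such eyes are failures. The size is conditional: 3.3% to 6.3% false success for 1% to 3% of eyes dropped as failures, and 2.6% to 3.3% if half would respond, against 2.3% with none dropped. These rest on assumed shares, independent eyes and exactly 54 and 86 measured eyes. With few explants the effect is small, though one eye can decide a result at the bound. The missing bounds for 87 to 96 eyes are a separate gap. It should be fixed, but the documents do not show that a material bias will occur.

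**What to change.** 1. Amend the FAS definition so that every eye whose study lens was permanently removed before Visit 5 stays in the primary denominator as a non-responder, whatever its later UCNVA, and make the SAP agree. State plainly that eyes missing for other reasons are excluded from the main rate, which is therefore still not a rate of all implanted eyes.
2. Prespecify a sensitivity analysis on the SES that counts every eye without Visit 5 UCNVA as a non-responder, with an exact confidence interval.
3. Analyse the Visit 3 and Visit 4 endpoints on implanted eyes with data at that visit.
4. State final bounds for the number of eyes actually analysed, for example the list in step 5. Say beside it that the bounds hold 2.5% only if the two eyes of a subject are independent. State that the interim is run on 54 eyes with Visit 5 results, and align Section 7.3 with this.

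**Cost.** Wording and one table. If 87.5% is the rate among eyes that keep the lens, item 1 multiplies it by (1 − share explanted). Two-stage power then falls from 81.7% to 74.5%, 66.4% and 57.7% with 1%, 2% and 3% explanted. If 87.5% is already a rate of implanted eyes, as the endpoint is worded, no power is lost. Item 2 should stay a sensitivity analysis. As the deciding rule on 96 eyes (bound 81), power would fall from 84.8% with none missing to 70.1%, 43.4% and 11.5% with 2%, 5% and 10% missing.

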#### Per Protocol Set:

The PPS contains data of each eye in the FAS without major protocol deviations. Protocol deviations are further classified in the SAP.

# 8.0 DATA QUALITY ASSURANCE

#### 8.1 Study Monitoring

STAAR Surgical (or its representatives/agents/designees) must be allowed to visit all study site locations to assess the data, quality, and study integrity in a manner consistent with applicable health authority regulations and internal Standard Operating Procedures (SOPs).

Prior to the start of the study, member(s) of STAAR Clinical and Medical Affairs Department (or designees) will review the protocol, CRF, regulatory obligations, and other material or equipment relevant to the conduct of the study with the Investigator/Sub-Investigator and relevant site personnel.

Monitoring visits and telephone consultations will occur as necessary during the course of the investigation to verify the following:

- the rights and well-being of subjects are protected
- the conduct of the investigation is in compliance with the currently approved protocol/amendment, ICH GCPs and EN ISO 14155 (2011) Clinical Investigation of Medical Devices for Human Subjects, EC requirements, and applicable local regulations
- the integrity of the data, including adequate study documentation
- the facilities remain acceptable
- the Investigator and site personnel remain qualified and able to conduct the study
- test article accountability

During the course of the study, if the Sponsor determines that an Investigator is non-compliant with the study plan and/or applicable regulatory requirements, the Sponsor will take action to secure compliance. In addition, the Sponsor may terminate the Investigator's participation in the study if appropriate, or if the Investigator remains non-compliant despite the Sponsor's actions.

# 8.2 Source Documentation

All medical information obtained at each study visit must be recorded in the subject's record (source documentation) in real time as it is collected. Source documentation consists of original subject documents, as well as data and records with information relevant to the subject and his/her participation in the study.

Examples of acceptable source documents include: hospital records, clinical and office charts, notes, or memoranda. The signed ICF, evaluation checklists, recorded data from automated instruments, and subject files. Source data also include information initially recorded in an electronic format (e.g., iTrace images, etc.).

Source documentation worksheets will be provided by the Sponsor to record pertinent information which are not part of the standard of care treatment for the particular study population to ensure that all critical study data are captured. The completed worksheets should then be incorporated into the subject's medical chart.

# 8.3 Case Report Forms and Data Verification

Subject data required by this protocol are to be recorded per standard of care at each clinical site and transcribed onto electronic CRFs. The Investigator and his/her study site personnel will be responsible for completing the CRFs. The Investigator is required to verify that all of the requested information is accurately recorded on the CRFs. All information requested on the CRFs needs to be supplied, including subject identification, date(s), assessment values, etc., and any omission or discrepancy will require explanation. All information on CRFs must be traceable to source documents if not otherwise specified in the Monitoring Plan for the study.

A STAAR Surgical designee will be responsible for reviewing and verifying the data recorded on the CRFs, utilizing the original source documentation and issuing queries as necessary for clarifications or discrepancies. The Investigator and study site personnel will be responsible for answering all queries. The CRFs will be submitted to STAAR Surgical via an electronic data capture system for quality assurance review and statistical analysis.

A copy of the CRFs will be retained by the Investigator at the conclusion of the study, who must ensure that it is stored in a secure place.

#### 8.4 Recording of Data and Retention of Documents

Subject data recorded on CRFs during the study will be documented in a coded fashion. The subject will only be identified by the subject number, and by their initials/year of birth if also required. Confidentiality of subject records must be maintained to ensure adherence to applicable local privacy regulations.

The Investigator must retain essential documents according to the applicable local regulatory requirements after the completion of the study, unless otherwise notified by the Sponsor.

Essential documents include but are not limited to the following:

- study protocol/amendments
- Protocol Signature Page signed and dated by the Principal Investigator
- EC approved blank as well as copies of all signed subject ICFs
- all EC approvals, correspondence and reports (e.g., SAE reports, protocol deviations, and safety updates)
- curriculum vitae and medical licenses for the PI and all sub-investigators (if applicable)
- regulatory documents (e.g., financial disclosure and DOA forms)
- source documents
- archive of CRFs
- Device Investigator Agreement
- investigational device accountability records
- relevant correspondence from and to the Sponsor
- any other documents relevant to the conduct of the study

In the event that the Investigator withdraws from the study (e.g., retirement, relocation), study records will be transferred to a mutually agreed upon designee (e.g., another Investigator, site EC). The Investigator will provide notice of such transfer in writing to STAAR Surgical.

# 8.5 Auditing Procedures

Audits of clinical research activities in accordance with the Sponsor's internal SOPs to evaluate compliance with the principles of GCP may take place. A regulatory authority may also wish to conduct an inspection (during the study or after its completion). If an inspection is requested by a regulatory authority and/or EC, the Investigator must inform the Sponsor immediately that this request has been made.

### 8.6 Ethics Committee Approval

The Investigator should ensure that participation in the study, in addition to the protocol, subject recruitment materials and the ICF to be used in this study are approved by their institution EC, or if not using their institution's EC, approved by the reviewing central EC prior to entering any subjects in the study. Documentation of EC approval of the study protocol and informed consent must be provided to the Sponsor

prior to initiation of the study and maintained during the course of the study. In addition, the Investigator must ensure that the reviewing EC has provided approval for any protocol amendments prior to implementation. If the amendment necessitates a revision to the ICF, the Investigator should ensure the revised form is also submitted to and approved by the Sponsor and the EC prior to reconsenting study subjects.

# 8.7 Publication of Results

All data generated as a result of this study will be regarded as confidential, until appropriate analysis and review by the Sponsor or its designee are completed. The results of the study may be published or presented by the Investigator(s) after the review by, and in consultation and agreement with the Sponsor, and such that confidential or proprietary information is not disclosed.

Prior to publication or presentation, a copy of the final text should be forwarded by the Investigator(s) to the Sponsor or its designee, for comment. Such comments shall aim to ensure the scientific integrity of the proposed publications and/or presentations and ensure that the data and material referring to STAAR Surgical products and activities receive fair, accurate, and reasonable presentation.

#### Study #CP17-01 - Protocol

# **APPENDIX A:** SCHEDULE OF VISITS AND PARAMETERS

All study tasks should be performed by qualified study site personnel as indicated on the delegation of authority log under the supervision of the Principal Investigator.

Shown below are all assessments to be done at the Preoperative, Operative, and each Postoperative Visit for the first surgical eye. A "B" in an assessment block indicates that the assessment is done for both the study eye alone and binocularly as well. All testing for the fellow eye is found in **Table 2**.

